### 9.6. Clinical Outcome Events

The following clinical outcome events will be captured in the study:

- Time from first dose to death (all cause)
- Time from first dose to liver-related death
- Time from first dose to liver transplant
- Time from first dose to MELD score  $\geq 15$  (for patients with MELD  $\leq 12$  at baseline)
- Time from first dose to earliest hospitalization for new onset or recurrence of:
  - variceal bleed
  - hepatic encephalopathy (as defined by a West Haven score of  $\geq 2$ )
  - spontaneous bacterial peritonitis (confirmed by diagnostic paracentesis)
- Time from first dose to uncontrolled ascites (diuretic resistant ascites requiring therapeutic paracentesis at a frequency of at least twice in a month)
- Time to first occurrence of any above listed clinical events

The incidence and time to first occurrence of any above listed clinical events will be summarized by treatment group using the log rank test stratified by the randomization stratification factor. The minimum and maximum time to clinical event will be presented. KM estimates of the

distribution of the time-to-event will be tabulated and graphed by treatment group. The tabulation will include the KM methodology using 25th, 50th (median), and 75th percentiles with associated 2-sided 95% CIs, as well as percentage of censored observations. The number and percent of patients censored and with events will be presented. The hazard ratio and 2-sided 95% CI will be estimated based on a Cox regression model stratified by randomization strata. The proportionality of hazards will be assessed using Schoenfeld residuals.

In addition, the incidence and time to each of the above clinical events, and the incidence and time to occurrence of HCC will be summarized by treatment group using the same methods as defined above.

For the time to event analyses, subjects who do not experience an event will be censored at the time of their last contact. Subjects with no data after randomization will be considered to have an event on Day 1 (first day of IP dosing). All time-to-event endpoints include only adjudicated events.

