### **Missing Data**

All available data of the subjects who withdraw from the study for any reasons will be analyzed. Missing data will be assumed to be missing at random. There will be no imputation of missing data for the analysis purpose. Change from baseline of an endpoint will be missing when either baseline value of the endpoint is missing or post-baseline value of the endpoint is missing.

Incomplete start and end dates for adverse events and concomitant medications are imputed as follows:

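### SAP Section 9.6 gives dosed subjects with no later data an unobserved event on Day 1 on every clinical outcome, against its own adjudicated-only rule

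*SAP*

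**What the plan says.** SAP Section 9.6 lists six single clinical outcomes timed from first dose: all-cause death, liver-related death, liver transplant, MELD of 15 or more (only for patients with baseline MELD of 12 or less), hospitalization for specified hepatic events, and uncontrolled ascites. It adds a composite of the first of these. Death and transplant are endpoints in their own right: "Time from first dose to death (all cause") and "Time from first dose to liver transplant".

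The composite gets incidence, a stratified log-rank test, Kaplan-Meier estimates and a stratified Cox hazard ratio. The section then applies the composite's methods to every single outcome and to HCC, whose results "will be summarized by treatment group using the same methods as defined above".

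Three sentences close the section and govern all of these analyses:

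- Event-free subjects: "subjects who do not experience an event will be censored at the time of their last contact".
- Subjects without data: "Subjects with no data after randomization will be considered to have an event on Day 1 (first day of IP dosing").
- Which events count: "All time-to-event endpoints include only adjudicated events".

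Section 9 runs the efficacy analyses on the ITT Population, which Section 4.2 restricts to randomized patients who took some study drug.

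**The concern.** A subject with no data carries no information about whether or when an event occurred. The rule nevertheless records an event, at the earliest possible time, and does not confine this to the composite. Followed literally, one subject enters the tables on Day 1 as a death, a liver-related death, a transplant, a hospitalization, an ascites event and an HCC at once.

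The adjudication sentence pulls the other way, since there is nothing for an adjudicator to review. One programmer could count the event and another drop it, and each could point to Section 9.6.

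If the events are counted, the treatment comparison shifts according to which arm happens to contain the subject. An OCA subject without data makes OCA look worse on death and decompensation, and a placebo subject makes it look better. The Section 9.6 death table could also disagree with the listing of adverse events leading to death in Section 10.3.4, which rests on actual records.

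**Working it through.** The SAP gives no event count, hazard ratio or power for these endpoints, so there is no figure of its own to reproduce.

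**Inputs from the SAP.** Section 3.3: about 50 patients, 1:1, so 50/2 = 25 per arm. Sections 4.2 and 9: a dose is required. Section 9.6: the rules above.

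**Assumed inputs.** The number k of affected subjects, all in one arm, and a true one-year event risk r equal in both arms. The SAP gives neither.

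**Who is affected.**
- Randomized but never dosed: outside ITT, with no dosing Day 1. Not affected.
- Dosed, with some later contact, then lost: censored at last contact. Not affected.
- Dosed, with nothing recorded afterwards: affected.

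**Endpoints per affected subject.** Six single outcomes + composite + HCC = 8 Day 1 events, counting hospitalization as one endpoint. If baseline MELD is above 12, the MELD endpoint does not apply and the count is 7.

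**Incidence.** Compared with censoring, k subjects add k/25 to the arm's incidence:

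| k | Added incidence |
|---|---|
| 1 | 4 points |
| 2 | 8 points |
| 3 | 12 points |

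With no true deaths, one such subject turns a reported mortality of 0% into 4%. For MELD of 15 or more, the addition is 1/m, where m is the number in the arm with baseline MELD of 12 or less. That denominator is below 25 unless everyone qualifies, and the addition is zero for a subject above 12.

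**Event-rate ratio, k = 1.** The affected subject contributes one event and almost no follow-up. Let T be the mean follow-up per remaining subject.

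- Affected arm: (24r + 1)/(24T)
- Other arm: 25r/(25T) = r/T
- Ratio: (24r + 1)/(24r) = 1 + 1/(24r)

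| Assumed r | Calculation | Ratio (true value 1) |
|---|---|---|
| 4% | 1 + 1/0.96 | 2.04 |
| 8% | 1 + 1/1.92 | 1.52 |
| 12% | 1 + 1/2.88 | 1.35 |
| 20% | 1 + 1/4.8 | 1.21 |
| 40% | 1 + 1/9.6 | 1.10 |
| 60% | 1 + 1/14.4 | 1.07 |

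**Check with a Cox model.** Simulation with 25 per arm, 336 days of follow-up, true hazard ratio 1 and 600 runs, unstratified, leaving out runs in which an arm had no event:

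| Assumed event rate | Median HR, k = 0 | k = 1 | k = 2 |
|---|---|---|---|
| 10% | 1.01 | 1.43 | 1.80 |
| 20% | 0.98 | 1.21 | 1.43 |
| 30% | 1.02 | 1.16 | 1.33 |

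For k = 1 the formula gives 1.42, 1.21 and 1.14, so the two agree closely.

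**Under censoring on Day 1.** Such subjects add 0 events and 0 percentage points to every endpoint.

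**The case against.** The strongest defence is that the rule will rarely, perhaps never, operate. Undosed subjects are outside ITT, and anyone seen even once after dosing is censored at last contact. Taken strictly, a dosing record is itself data after randomization, which could leave nobody in the category. This stands as a limit on reach. It also shows that the trigger (randomization) does not match the time origin (first dose). A reader might infer from the rule that any patient lost to follow-up is reported as dead or transplanted; the censoring sentence rules that out.

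A reader might also see a contradiction with Appendix A, Missing Data: "There will be no imputation of missing data for the analysis purpose". That is weak. Appendix A is a general convention, and the SAP makes specific exceptions elsewhere, for example by treating adverse events of missing severity as severe (Section 10.3.4). A specific Section 9.6 rule may depart from a general one. The conflict with the adjudication sentence is different, because both sentences govern the same endpoints.

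That conflict also means that false deaths are not certain: if the adjudication sentence prevails, the imputed event drops out. This is fair, but it describes an ambiguity that needs resolving.

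The larger ratios need low risks. The composite in Child-Pugh B and C patients, with treatment continuing past 48 weeks, may carry a much higher cumulative risk, and at 40% to 60% the ratio is only 1.10 to 1.07. This stands for the composite. Rarer single components may lie lower on the scale, but the SAP does not say.

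Finally, counting non-evaluable subjects as failures is a recognised worst-case convention. It can be argued for a composite. It does not suit death, transplant and HCC taken singly, and it is not conservative when the subject is on placebo.

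**Conclusion.** The rule is wrong as written. It assigns unobserved events to every clinical outcome endpoint and cannot be applied together with the adjudicated-only sentence beside it. Its reach is narrow: dosed subjects with no later data, possibly none.

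If one occurs, the distortion is about 4 percentage points on each endpoint for which the whole arm of 25 is eligible. The event-rate ratio moves from 1 to roughly 1.5, 1.2 or 1.1 at assumed one-year risks of 8%, 20% or 40%. These figures assume 25 per arm, equal true risk, one affected subject in one arm, and no stratification, whereas the planned Cox model is stratified.

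A reader might infer a threat to the trial's main safety conclusion. The document does not support that. Section 2.1.3 makes these endpoints exploratory, Section 2.2 states no formal hypothesis, and the adverse event outputs are built from actual records. Severity is moderate.

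**What to change.** In SAP Section 9.6, replace the Day 1 event sentence with: *Subjects with no data after first dose will be censored on Day 1.* This removes the conflict with the adjudication sentence and aligns the trigger with the time origin.

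If a worst-case view is wanted, specify it as a labelled sensitivity analysis of the composite only, and state that its imputed events are exempt from adjudication.

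The cost is one sentence, with no new data and no effect on sample size. It should be settled before database lock and unblinding, so that the choice cannot depend on which arm holds an affected subject.

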## 10. SAFETY ANALYSES

Safety analyses include exposure to study treatment, treatment-emergent adverse events, clinical labs, electrocardiograms (ECGs), vital signs, and any abnormal findings observed during physical examinations after study enrollment and through discontinuation of study treatment +30 days. Safety analyses will be performed using the Safety population including by treatment groups, as defined in [Section 4.3](#) and pooled across all active dose levels. No inferential comparison of safety endpoints will be performed, unless otherwise specified.

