## 2. STUDY OBJECTIVES AND HYPOTHESES

### 2.1. Study Objectives

#### 2.1.1. Primary Objective

- To evaluate the PK of OCA and its conjugates, glyco-OCA and tauro-OCA, and OCA metabolite glucuronide compared with placebo
- To evaluate the safety and tolerability of OCA treatment compared with placebo

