## 2.2. Hypotheses

The primary objective of this study is to evaluate the PK of OCA and its conjugates, safety and tolerability of OCA compared with placebo. Therefore, there is no formal statistical hypothesis to be tested.

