#### 10.3.4. TEAE Analyses

The counts and percentages of subjects experiencing a TEAE and TEAEs by PTs and SOCs in the following categories will be presented by study treatment arm:

All AE summaries will be restricted to TEAEs. Each AE summary will be displayed by treatment group for DB phase, DBext phase, and combined. Summaries that are displayed by SOC and PT will be ordered by descending order of incidence of SOC and PT within each system organ class.

Summary tables of the following TEAEs will be presented:

- Overall summary of TEAEs
- Patient incidence of TEAEs and the total number of entries by SOC and PT. This summary will be repeated for subgroups specified in [Section 10.10](#).
- Patient incidence of TEAEs by SOC, PT, and highest severity. At each level of patient summarization, a patient is classified according to the highest severity if the patient reported 1 or more events. AEs with missing severity will be considered severe for this summary.
- Patient incidence of TEAEs by SOC, PT, and closest relationship to IP (Related/Not Related). Related AEs are those with relationships reported as “Definite,” “Probable,” or “Possible,” and unrelated AEs are those with relationships reported as “Unlikely” or “Not Related”. At each level of patient summarization, a patient is classified according to the closest relationship if the patient reported 1 or more events. AEs with a missing relationship will be considered related for this summary.
- Patient incidence of serious TEAEs and the total number of entries by SOC and PT.
- Patient incidence of TEAEs leading to IP withdrawal or study discontinuation by SOC and PT. This is a subset of the AEs where Action Taken with Study Treatment is checked as “Drug Withdrawn” or where “Patient Discontinued from Study” is checked on the eCRF.
- Patient incidence of COVID-19 related TEAEs.

Patient incidence will be summarized as subject counts and percentages unless otherwise specified.

The number of AEs and events per 100 patient years will be summarized by SOC and PT.

- Individual patient years = (the last recorded study visit date – first dose date +1)/365.25  
where: the last recorded study visit date = end of study date recorded on end of study CRF page for that patient
- Total patient years on study = sum of all individual patient years within the Safety Population
- Events per 100 patient years =  $\frac{\text{Number of Event} \times 100}{\text{Total Patient Years on Study}}$

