The analysis of time to first onset of treatment-emergent pruritus AE, time to onset of the first moderate or severe treatment-emergent pruritus, and onset of the first severe treatment-emergent pruritus will include the number of patients with pruritus (first onset, first moderate or severe, first severe), the number of patients without pruritus (censored), and the minimum and maximum times in days. KM estimates will be calculated by treatment group. The tabulation will include the KM estimate methodology using 25th, 50th (median), and 75th percentiles of the medians and corresponding 2-sided 95% CIs, if the medians can be estimated as well as percentage of censored observations. KM estimates will be plotted as a “survival curve” for each treatment group.

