The analysis of time to first onset of treatment-emergent fatigue AE, time to onset of the first moderate or severe treatment-emergent fatigue, and onset of the first severe treatment-emergent fatigue will include the number of patients with fatigue (first onset, first moderate or severe, first severe), the number of patients without fatigue (censored), and the minimum and maximum times in days. KM estimates will be calculated by treatment group. The quartiles, including the median time-to-event and their corresponding 2-sided 95% CIs, will be presented. KM estimates will be plotted as a “survival curve” for each treatment group.

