### **General Methods**

- Summaries will be presented for each treatment and overall for subjects disposition, demographics and baseline characteristics, medical history, disease history, prior medications, and historical procedures summary tables. Summaries will be presented for each treatment for other tables.
- All subjects and relevant data entered into the database will be included in subject data listings, including screen failures, where applicable.
- All data listings that contain an evaluation date will contain a relative study day as defined in below.
- For categorical variables, summary tabulations of the number and percentage of patients within each category of the parameter will be presented. Percentage calculations will be based on non-missing data, unless otherwise specified. Percentages are rounded to 1 decimal place, unless otherwise specified. The category for missing data will not have percentage.
- For continuous variables, the number of patients, mean, standard deviation (SD), standard error of the mean (SE), median, Q1, Q3, minimum, and maximum values will be presented. The precision of summary statistics, unless otherwise, specified will be as follows:
  - minimum, maximum: same decimal place as the raw data,
  - mean, median, Q1, and Q3: 1 more decimal place than the raw data,
  - SD and SE: 2 decimal places more than the raw data.
- In general, the decimal places should not exceed 3 decimal places unless appropriate. 95% confidence intervals (CIs) will be provided and will be rounded to 1 decimal place.

- For results from an analysis of covariance (ANCOVA) model or a mixed model repeated measures (MMRM), least square (LS) mean and LS mean difference will be presented with one decimal place, and standard error (SE) of LS means and SE of LS mean difference will be presented with two decimal places.
- p-value will be presented with 3 decimal places.
- Time-to-event data will be summarized using Kaplan-Meier (KM) methodology using 25th, 50th (median), and 75th percentiles with associated 2-sided 95% CIs.

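### Safety against placebo is a primary objective, but no OCA-placebo difference or interval is planned for the adverse event incidences and rates

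*SAP*

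**What the plan says.** Section 2.1.1 lists as a primary objective "To evaluate the safety and tolerability of OCA treatment compared with placebo". Section 2.2 says of the primary objectives: "Therefore, there is no formal statistical hypothesis to be tested". Section 3.3 adds 20 patients to a PK requirement of 30 so as to support safety and efficacy evaluations, giving about 50 in total, randomized 1:1.

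Section 10 sets the rule for safety: "No inferential comparison of safety endpoints will be performed, unless otherwise specified". Section 10.3.4 fixes the measures for TEAEs: "Patient incidence will be summarized as subject counts and percentages unless otherwise specified", and "The number of AEs and events per 100 patient years will be summarized by SOC and PT". The tables cover all TEAEs, severity, relationship, serious TEAEs and TEAEs leading to withdrawal. Section 10.3.3 defines adverse events of special interest (the decompensation events), but Section 10.3.4 names no table for them.

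Other parts of the plan do state precision:
- Section 10.3.5 gives Kaplan-Meier percentiles for time to pruritus with "corresponding 2-sided 95% CIs, if the medians can be estimated as well as percentage of censored observations".
- Section 10.3.6 does the same for fatigue: "The quartiles, including the median time-to-event and their corresponding 2-sided 95% CIs, will be presented".
- General Methods in Appendix A specifies: "For continuous variables, the number of patients, mean, standard deviation (SD), standard error of the mean (SE), median, Q1, Q3, minimum, and maximum values".
- Section 9.6 plans stratified log-rank tests and Cox hazard ratios with 95% intervals for adjudicated clinical outcome events.
- Section 9.3 gives liver biochemistry, a secondary endpoint, a between-arm difference with SE, 95% interval and p-value.

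**The concern.** A comparative primary objective needs an estimate of the comparison. For adverse events, the plan prints two columns of percentages and leaves the contrast to the reader. The exception clause in Section 10 is never used for an adverse event contrast.

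In a trial of this size, bare percentages mislead in both directions. Equal or zero counts look reassuring while a substantial excess remains possible. A handful of extra events looks alarming while no difference remains possible. Without an interval, the report does not show how large an excess of serious, severe or treatment-limiting events the data fail to exclude, which is one of the more useful things a 50-patient safety comparison can offer.

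The emphasis is also uneven: secondary biochemistry receives a full between-arm estimate with its precision, and the primary adverse event comparison does not.

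**Working it through.** **Sample size.** Section 3.3 gives 20 OCA + 10 placebo + 20 additional = 50, which reproduces the stated total. At 1:1 this is 50/2 = 25 per arm. The SAP states no power or precision for safety.

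**Assumption.** The SAP gives no adverse event rates, so the counts below are assumed and cover a range. They are not predictions.

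**Zero events in one arm.** The exact two-sided 95% upper limit is 1 - 0.025^(1/25) = 13.7%.

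**Risk difference, Newcombe 95% interval.** Each arm's Wilson limits are [p + z²/2n ± z√(p(1-p)/n + z²/4n²)] / (1 + z²/n), with z = 1.96. For d = p1 - p2, the lower limit is d - √[(p1-l1)² + (u2-p2)²] and the upper limit is d + √[(u1-p1)² + (p2-l2)²].

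Worked case, 5/25 v 5/25: the Wilson limits are 0.089 and 0.391 in each arm. The half-width is √[(0.200-0.089)² + (0.391-0.200)²] = 0.221, so the interval is -22.1 to +22.1 points.

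| OCA v placebo, of 25 each | Difference (points) | 95% interval |
|---|---|---|
| 0 v 0 | 0 | -13.3 to +13.3 |
| 3 v 1 | +8 | -9.4 to +26.3 |
| 5 v 2 | +12 | -8.3 to +32.0 |
| 5 v 5 | 0 | -22.1 to +22.1 |
| 10 v 5 | +20 | -5.3 to +42.2 |
| 15 v 10 | +20 | -7.2 to +43.5 |

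**Rate ratio.** With equal person-time and simple Poisson counts, the interval is exp[ln(e1/e2) ± 1.96√(1/e1 + 1/e2)]. For 10 v 5 events the ratio is 2.0, interval 0.68 to 5.85. For 20 v 10 events it is 2.0, interval 0.94 to 4.27.

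**Would tests serve better?** Normal-approximation power for a 20-point difference at 25 per arm, two-sided 5%, is 42% for 10% v 30%, 33% for 20% v 40%, and 29% for 40% v 60%. Tests would usually miss such a difference, so intervals are the more useful output.

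**By Child-Pugh class.** Section 3.3 requires at least 20% CP-C. At that minimum, 0.20 × 50 = 10 patients, about 5 per arm. For 0/5 v 0/5 the Newcombe limits are ± z²/(n + z²) = 3.84/8.84, about ±43 points. Intervals by class would not be informative.

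**The case against.** A reader might infer that the plan forbids every interval on safety and leaves the primary safety question with no measure of uncertainty. The documents do not support that. The rule in Section 10 concerns inferential comparison and carries an exception clause. Sections 10.3.5 and 10.3.6 plan 95% intervals within each arm, and Appendix A gives standard errors for continuous data, which include safety laboratory values and vital signs. Section 9.6 provides between-arm hazard ratios with intervals for the gravest outcomes: death, transplant, hospitalization for variceal bleed, encephalopathy or peritonitis, and uncontrolled ascites. Filing these under efficacy does not remove the information.

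It is also fair to say that the absence of a safety hypothesis is declared in Section 2.2, that side-by-side summaries are a form of comparison, that the SAP nowhere promises an interval for adverse event differences, and that a reader with the counts could compute one. All of this stands, so the point is neither a contradiction nor a wrong number.

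It does not close the gap. The pruritus and fatigue intervals describe time percentiles within an arm, not a contrast, and the 25th percentile is not reached if fewer than about a quarter of an arm has the event. Section 9.6 is limited to adjudicated events and, for three decompensation types, to hospitalizations. The special-interest list in Section 10.3.3 is wider: variceal bleeding whether or not hospitalized, new or worsening ascites, hepatorenal syndrome or acute kidney injury, hyponatremia, and a 3-point MELD rise. Serious and severe TEAEs and withdrawals as categories lie outside Section 9.6. The remark in General Methods that 95% intervals will be provided sits in a rounding rule and names no estimate. Intervals computed afterwards by readers lack a pre-specified list of events.

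**Conclusion.** The point holds in a limited form. For TEAE incidences and rates, a central part of a primary objective framed against placebo, the SAP plans no OCA-placebo difference or ratio and no interval, while a secondary endpoint gets both. The decision not to test safety hypotheses is a legitimate, stated choice and is not disputed.

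On assumed counts with 25 per arm, the unreported uncertainty is about ±13 points when neither arm has an event, ±22 points at 5 v 5, and about 48 to 51 points of total width around a 20-point difference. The real widths depend on the observed counts and on how close the arms come to 25. This is a worthwhile low-cost improvement; no planned analysis is invalidated.

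**What to change.** Replace the sentence in Section 10 with wording such as:

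*Safety endpoints will not be subject to hypothesis tests. For serious TEAEs, severe TEAEs, adverse events of special interest, TEAEs leading to IP withdrawal, any pruritus and severe pruritus, the exact 95% CI of incidence in each arm and the OCA-placebo risk difference with its Newcombe 95% CI will be presented descriptively for the 48-week DB phase. For the combined DB and DBext period, where follow-up differs between patients, the difference or ratio of events per 100 patient-years will be presented with a 95% CI.*

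The period has to be named because Section 10.3.4 reports three (DB, DBext, combined), and Section 3 lets extension treatment run until the last patient finishes 48 weeks and the database is locked. A crude risk difference over the combined period would ignore unequal follow-up. The planned rate counts events, so one patient can contribute several; the rate interval should allow for this, since a simple Poisson interval may then be too narrow. Death and transplant can stay with Section 9.6. Do not add separate intervals by Child-Pugh class. Fix the list before database lock, which Section 1 already sets as the deadline for the SAP.

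The cost is one amended paragraph and one additional table. The drawbacks are wide intervals on display and several intervals without multiplicity control, which a footnote calling them descriptive should state.
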